With the advent of targeted therapies, recent progress has been made in developing effective treatment options for mRCC patients. Research on the molecular pathobiology of advanced/metastatic RCC has identified the VEGF /VEGF receptor (VEGFR) axis and the phosphatidylinositol-3-kinase (PI3K)/mammalian target of rapamycin (mTOR) pathway lying downstream (the "angiogenesis axis") as clinically relevant targets [13-15]. The VEGF/VEGFR axis plays a critical role in tumor growth and survival [14].

Inhibitors of this pathway include the multitargeted receptor tyrosine kinase inhibitors (TKI) sunitinib (Sutent®, Pfizer Inc.), sorafenib (Nexavar®, Bayer HealthCare/Onyx Pharmaceuticals), pazopanib (Votrient®, GlaxoSmithKline Inc) and axitinib (Inlyta®, Pfizer Inc), the VEGF

Axitinib, Inlyta[®]
A4061078 NON-INTERVENTIONAL STUDY PROTOCOL
ADONIS Amended V13
28 Sept 2017

ligand-binding monoclonal antibody bevacizumab (Avastin®, Genentech, Inc.), usually given in combination with Interferon-alpha, and the mammalian target of rapamycin (mTOR) kinase inhibitors temsirolimus (Torisel®, Pfizer Inc) and everolimus (Afinitor®, Novartis). Cytokines have now been largely superseded by novel agents targeted against specific components of the pathways involved in tumor growth and angiogenesis, such as VEGF/VEGFRs [16.17].

Gap 1 :

Axitinib (Inlyta®) is a small molecule VEGFR TKI and has recently been approved in Europe. Axitinib is indicated (in Europe) "for the treatment of adult patients with adv/mRCC after failure of prior treatment with sunitinib or a cytokine" [1]. The AXIS phase III randomized clinical trial demonstrated superior efficacy of axitinib relative to sorafenib in second line treatment. The overall PFS by independent review (primary endpoint) was 6.7 versus 4.7 months. In patients previously given sunitinib alone or cytokine alone, the PFS were 4.8 versus 3.4 months and 12.1 versus 6.1 months, respectively. The PFS of axitinib post sunitinib was 6.5 months when assessed by investigators [2].

The AXIS study has established axitinib (Inlyta®) as a standard of care in 2nd line mRCC patients. However, the real life impact of second line Axitinib post Sunitinib remains to be established and the non-interventional real-life study ADONIS will lead to an increased knowledge and answer important questions about Axitinib in terms of efficacy, safety, dose titration practices and quality of life.

Gap 2 :

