8.1.1. Study endpoints

Primary endpoints:

Progression Free Survival (PFS):

- PFS for patients with adv/mRCC receiving AXI in 2nd line post SU as defined as the time from when the patient receives the first dose of AXI to the time of progression or death due to any cause, whichever occurs first
- Combined PFS for patients with adv/mRCC receiving the SU-AXI sequence as defined
 as the time from when the patient receives the first dose with SU in first line, until
 progression or death due to any cause with AXI in 2nd line, whichever occurs first during
 the SU-AXI sequence

(Time to Treatment Failure) TTF:

- TTF for the AXI 2nd line as defined as from when the patient receives the first dose of AXI to the time of AXI discontinuation (date completed by the physician).
- TTF for the SU-AXI sequence as defined as the time from when the patient receives the first dose with SU in first line to the time of AXI discontinuation (date completed by the physician).

Secondary endpoints:

- Objective Response Rate (ORR) for adv/mRCC patients receiving AXI in 2nd line post SU defined as the percentage of patients with confirmed complete response (CR) or confirmed partial response (PR) according to RECIST criteria v1.1.
- Overall survival (OS) for adv/mRCC patients receiving SU in first line followed by AXI in 2nd line as measured from date of first SU dose to the date of death of any cause. The OS median and the overall survival at month 24 (24 month OS) will be measured.
- Time to strategy failure (TSF) for patients receiving the SU-AXI sequence is defines as the time from when the patient receives the first dose with SU in first line to the time of AXI discontinuation (date completed by the physician) without the time between discontinuation of SU and start of AXI.
- Description of real life usage of flexible dosing across Europe with description of treatment schedules (dosing change, dosing schedule, average dose received during the period treatment)

- Proportion of titrated patients: titration is defined as described in the SmPC. A patient is considered as titrated when an AXI dose increase is maintained for at least 4 weeks.
- PFS for titrated and non-titrated patients when they receive AXI in 2nd line post SU
- Efficacy parameters (PFS, OS) for the combined 1st line SU 2nd line sequences according to the second line post Sunitinib (other than SU-AXI):
 - SU in 1st line other TKI in 2nd line (sorafenib, pazopanib)

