8.2. Setting

The study will enroll patients according to the eligibility criteria in participating countries across Europe. The recruiting centers will be representative of each country involved in terms of care management systems, of size and of practices (at least when performing feasibility).

Any patient who meets the eligibility criteria will be invited to participate in the study with no selection by the investigators. The enrollment visit will be performed at the time of the patients' inclusion, after the patients' acceptation of enrollment in the study.

Data will come from medical records and will be collected in routine clinical practice. The enrollment visit will comprise a first section on patients' eligibility for every patient whatever pool they belong to and a second section depending on the treatment started (SU or AXI) at the inclusion.

For patients enrolled in the study when AXI is started as a 2^{nd} line therapy, a retrospective section will be completed at patients' inclusion, to collect data on SU 1^{st} line treatment.

For patients who start AXI when SU is discontinued during the study, the AXI initiation visit will resume baseline data that need to be updated.

Follow-up will be ensured during visits in the context of usual patients' care management (non-interventional study). No visits will be required by the protocol of the study. As long as the

patients are treated with SU or AXI, every visit to the center will be recorded. In accordance with ESMO guidelines and physicians clinical practice is real life, follow-up visits are approximately expected:

- during SU treatment: every 6 weeks (every cycle) with tumor assessment approximately every 3 months with respect to the clinical practice
- during AXI treatment: every 4 weeks (every cycle) with tumor approximately assessment every 2 months with respect to the clinical practice

[figure not shown]
When patients come off SU treatment (i.e. are not receiving AXI) or come off Axitinib (after receiving the SU-AXI sequence) they will be followed up every 6 months (separate form) for survival until the end of the study.

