8.5. Study size

The primary endpoints of this study in patients with adv/mRCC are PFS and TTF for patients receiving AXI in 2nd line and the combined PFS and TTF for patients receiving the SU-AXI sequence. In this non-interventional real life study, the objective is only descriptive and the sample size will rely on the precision of the estimate.

The expected precision of the median PFS can be calculated with the Greenwood's formula. The formula provides an estimate of the variance of S(t) (Kaplan-Meier estimate) as follows:

$$\hat{Var}[\hat{S}(t)] = [\hat{S}(t)]^2 \sum_{j:t_i \leq t} \frac{d_j}{n_j(n_j - d_j)}$$

where tj is the times of events, dj the number of events at these times and nj the sample size at risk.

Assuming the absence of right-censoring before the median survival and the occurrence of a single event for each event time, Greenwood's formula for median survival can be simplified as follows:

$$\hat{Var}[\hat{S}(t)] = \frac{0, 5^2}{n}.$$

The different variances and CI of S(t) can therefore be calculated as a function of n and accuracy.

		Variance	
s(t) ²	n	$(s(t)^2/n)$	Accuracy
	150	0.001666667	0.080
	175	0.001428571	0.074
	200	0.00125	0.069
	225	0.001111111	0.065
0.25	250	0.001	0.062
	300	0.00083	0.056
	350	0.0007143	0.052

Table 2: sample size and accuracy of PFS

Inclusion of 350 patients with the SU-AXI sequence will allow demonstration of median progression free survival as well as time to treatment failure with an accuracy of 5.2%.

The SU-AXI 350-patient sample is expected to comprise two thirds of patients enrolled in the AXI 2nd line pool (approx. 225 patients) and one third of patients enrolled in the SU 1st line pool then receiving an AXI 2nd line (approx. 125 patients).

This last group (125 patients) implies initial inclusion of 525 patients in the SU 1st line pool. Based on current EU market research and 2014 forecasts, it is expected that 68% of the SU 1st line pool has a 2nd line treatment (357 patients); and that 35% are expected to initiate 2nd line treatment with AXI (125 patients).

ADONIS is therefore targeting approximately 750 patients: 225 in the AXI pool and 525 in the SU pool. These estimates will allow for an approximate SU-AXI 350- patient group to meet primary outcome objectives and a SU – other 2nd line treatment group of 230 patients to meet secondary objectives.

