8.7.1. Efficacy Analysis

Progression-Free Survival (PFS)

Combined PFS of the SU-AXI sequence is defined as the time from when the patient receives the the first dose with SU in first line, until progression or death due to any cause with AXI in 2nd line, whichever occurs first during the SU-AXI sequence. PFS in patients receiving AXI in 2nd line is defined as the time from when the patient receives the first dose of AXI to the time of progression or death due to any cause, whichever occurs first.

Patients who remain progression free at the end of AXI treatment will be evaluated until death, disease progression or the start of a new anticancer therapy.

For the primary endpoints, PFS will be assessed using the Kaplan-Meier method. This method will be applied to derive, survival curves, median event time and a 95% confidence interval for the median.

Kaplan-Meier estimates will also be provided for sub-group analysis of interest:

- Titrated and non-titrated patients, defined in the following section (titration description section), receiving AXI in 2nd line
- Patients receiving AXI in 2nd line post SU depending on the response to SU in 1rst line.
- Country cohorts where feasible (pool size)
- SU 2nd groups depending on the 2nd line treatment :
 - O SU in 1st line- AXI in 2nd line,
 - o SU in 1st line other TKI in 2nd line (sorafenib, pazopanib)
 - O SU in 1st line / mTOR in 2nd line. (temsirolimus, everolimus)

Potential influences of baseline patient characteristics (eg, age, sex, MSKCC risk group) on the primary PFS will be evaluated by Cox proportional regression method.

Time to Treatment to Failure (TTF) and Time to Strategy Failure (TSF)

TTF for the AXI 2nd line is defined as from when the patient receives the first dose of AXI to the time of AXI discontinuation (date completed by the physician) whatever the reason for discontinuation is and whatever the following therapeutic strategy. In case of death while the patient is still treated with AXI, date of death will be considered as date of discontinuation.

TTF for the SU-AXI sequence is as defined as the time from when the patient receives the first dose with SU in first line to the time of AXI discontinuation (date completed by the physician).

TSF for SU-AXI sequence is defined as the time from when the patient receives the first dose with SU in first line to the time of AXI discontinuation (date completed by the physician) without the time between discontinuation of SU and start of AXI.

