4.2 STATISTICAL DECISION RULES

No statistical test will be performed. Whenever relevant, a two-sided 95% confidence interval will be provided.

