The Clinical Benefit Rate (CBR) will be the proportion of patients with a CR, PR or Stable Disease according to RECIST criteria from the start to the end of Axitinib treatment (cf. CRF page 29).

PFIZER CONFIDENTIAL

Page 16 of 41

Patients who die, progress, or drop out for any reason prior to reaching a CR, PR or SD will be counted as non-responders in the assessment of CBR.

All assessments following an assessment of PD will be excluded from the derivation of CBR.

- Objective Response Rate (ORR) under TKI in 2nd line post Sunitinib

ORR is defined as the percentage of patients with complete response (CR) or partial response (PR) as best response under TKI treatment (cf. CRF page 36).

- Clinical benefice Rate (CBR) under TKI in 2nd line post Sunitinib

The Clinical Benefit Rate (CBR) will be the proportion of patients with a CR, PR or Stable Disease as best response under TKI treatment (cf. CRF page 36).

- Objective Response Rate (ORR) under mTOR in 2nd line post Sunitinib

ORR is defined as the percentage of patients with complete response (CR) or partial response (PR) as best response under mTOR treatment (cf. CRF page 36).

- Clinical benefice Rate (CBR) under mTOR in 2nd line post Sunitinib

The Clinical Benefit Rate (CBR) will be the proportion of patients with a CR, PR or Stable Disease as best response under mTOR treatment (cf. CRF page 36).

- Objective Response Rate (ORR) under IO in 2nd line post Sunitinib

ORR is defined as the percentage of patients with complete response (CR) or partial response (PR) as best response under IO treatment (cf. CRF page 36).

- Clinical benefice Rate (CBR) under IO in 2nd line post Sunitinib

The Clinical Benefit Rate (CBR) will be the proportion of patients with a CR, PR or Stable Disease as best response under IO treatment (cf. CRF page 36).

- Objective Response Rate (ORR) for Sunitinib received in 1st line

ORR is defined as the percentage of patients with complete response (CR) or partial response (PR) as best response under Sunitinib treatment (cf. CRF page 12 for patients included at time of Sunitinib initiation, cf. CRF page 26 for patients included at time of Axitinib initiation).

- Clinical benefice Rate (CBR) for Sunitinib received in 1st line

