8.1.1 Descriptive Methods

Descriptive analysis of qualitative and ordinal variables will comprise the number and percentage of each category. Percentages will be calculated on the number of all available data, excluding missing data.

Descriptive analysis of quantitative variables will present the mean, the standard deviation (SD) as well as the median, quartile 1, quartile 3, min and max values.

The 95% confidence intervals will be presented for main endpoints. The 'exact' Clopper-Pearson confidence interval will be provided to assess 2-sided 95% confidence interval for main binomial proportions (e.g. ORR rate).

The number of missing values will be reported in the results table for each variable.

8.1.2 Survival Analysis Methods

The survival functions (for PFS, TTF, TSF, OS) will be estimated with the Kaplan-Meier method. The survival function S(t) is the probability that the event (treatment discontinuation, death or progression) does not occur before a specified time.

This method will be applied to derive, survival curves, median event time and a 95% confidence interval for the median survival time (time at which half the analyzed patients have presented the event). Survival curves will give an idea of whether or not the groups are proportional (i.e. the survival functions are approximately parallel). For OS, the share of patients alive at 24 months will also be measured.

The log-rank test of equality across strata will be used to compare survival curves for categorical variables (sub-groups of interest). For continuous variables, a univariate Cox proportional hazard regression will be used.

For analyses of prognostic factors of survival time, multivariate Cox proportional hazard regressions will be performed.

8.1.3 Strategy of Variable Selection in a Cox Model for PFS Analysis

The strategy of selection of variables in multivariate models will consist in: *Step 1: Selection of initial factor*

In a first step, the association between the PFS and each potential factor will be analyzed using

- A Log-Rank test (PROC LIFETEST under SAS 9.4) for categorical factors. Kaplan-Meier curves will also be presented in order to give an idea of whether or not the corresponding groups are proportional (i.e. the survival functions are approximately parallel)
- a univariate Cox proportional hazard regression (PROC PHREG under SAS 9.4) for continuous factors

Only significant factors at the 25% threshold will be retained for the initial model.

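### The planned side-by-side PFS curves for SU-AXI, SU-other TKI and SU-mTOR rest on unlike progression capture and unlike enrolment routes, and nothing visible in the plan aligns them

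*Protocol*

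**What the plan says.** **Display.** Protocol 8.7.1 gives Kaplan-Meier PFS for sub-groups of interest, among them "SU 2nd groups depending on the 2nd line treatment": axitinib, other TKI (sorafenib, pazopanib) and mTOR (temsirolimus, everolimus). The related endpoint bullet in Protocol 8.1.1 ("Efficacy parameters (PFS, OS) for the combined 1st line SU 2nd line sequences according to the second line post Sunitinib") is restricted to sequences other than SU-AXI, so 8.7.1 is where the three groups meet.

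**Follow-up.** Protocol 8.2 expects axitinib visits about every 4 weeks and tumour assessment about every 2 months. For patients off sunitinib and not on axitinib, "they will be followed up every 6 months (separate form) for survival until the end of the study". The CRF page for sunitinib discontinuation sends patients starting another drug to that long-term form (Annex 1, section 5). The form holds, per drug and line, start and end by month and year, best response, and reason for stopping, with a date if the reason is progression. It also records death.

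**SAP rules.** SAP 6.1.1 dates SU-AXI progression from the first tumour assessment showing it at an axitinib follow-up visit. Response on another TKI is taken "as best response under TKI treatment (cf. CRF page 36"), the page the SAP cites for long-term follow-up.

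**Entry.** Protocol 8.5 expects 225 patients enrolled at axitinib start and 525 at sunitinib start. About 125 of the latter go on to axitinib and about 230 to another second line.

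**Testing.** SAP 4.2: "No statistical test will be performed". SAP 8.1.2: "The log-rank test of equality across strata will be used to compare survival curves for categorical variables (sub-groups of interest").

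**The concern.** Three Kaplan-Meier curves in one display invite the reader to compare them, and the sequencing question in Protocol 6 (Gap 3) encourages this. Two features of the design can separate the curves when the drugs do not differ.

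- **Capture.** Progression with treatment continued is an event for axitinib if a scan shows it. On another second-line drug it has no dated field on the long-term form. Progression would then look later or rarer in the comparators.
- **Entry.** The clock starts at the first sunitinib dose. Patients enrolled at axitinib start may bring a sunitinib period of any length. Those enrolled at sunitinib start contribute to a second-line curve only if sunitinib ends before data collection does. All comparator patients come by that second route, so long sunitinib durations are under-represented there.

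The visible plan has no adjusted model between sequences: the Cox model in SAP 8.2.2 is within SU-AXI. The limitations in Protocol 8.9.4 cover differences between sites, not between second-line groups. If the log-rank sentence in SAP 8.1.2 is applied here, a p-value would be attached to a contrast that partly reflects the design.

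**Working it through.** **Step 1. The plan's own figures (Protocol 8.5).**

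- 525 × 0.68 = 357 reach second line; 357 × 0.35 = 124.95, or about 125 on axitinib; 357 − 125 = 232, against 230 stated.
- 225 + 125 = 350; 225/350 = 64% enter at axitinib start.
- Half-width at the median: 1.96 × √(0.25/350) = 0.052, as stated.

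**Step 2. Capture, side by side.**

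| | Axitinib | Other second line |
|---|---|---|
| Form | every recorded visit | long-term form, every 6 months |
| Dated assessments | yes | no |
| Progression, drug continued | dated event | no dated field |
| Progression as reason for stopping | dated | dated |
| Progression after a stop for another reason | not an event; censored at stop | no dated field |
| Death | recorded | recorded |

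The third row is the main asymmetry. SAP 6.1.1 also refers axitinib progression without a tumour assessment to data review, whereas progression dated at stopping is the only dated kind for the comparators.

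*Illustration, with no true difference.* Assumptions: exponential times; sunitinib median 8, 11 or 14 months; second-line median 4.8 or 6.5 months; 350 v 230 patients; axitinib progression found at 2-monthly scans; clock from first sunitinib dose; no censoring other than that stated. HR is SU-AXI against the comparators.

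| Comparator progression date | HR | Nominal 5% log-rank rejects |
|---|---|---|
| Complete, similar scans | 0.99–1.01 | 4–6% |
| Date of the 6-monthly form used instead | 1.09–1.16 | 17–44% |
| 80% recorded, rest censored at progression | 1.23–1.26 | 63–72% |
| 60% recorded, rest censored at progression | 1.62–1.67 | about 100% |

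The documents do not show which row applies.

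**Step 3. Entry route.** Data collection runs from 1 February 2014 to 30 April 2021, 86.9 months, taken as 87. Assume exponential sunitinib time T with rate λ = ln 2/median, entry a uniform over 54 months, and second line observed in the sunitinib-start route only if T < 87 − a.

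Share removed = (e^(−33λ) − e^(−87λ)) / (54λ), where 33 = 87 − 54:

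- median 8: (0.0573 − 0.0005)/4.679 = 1.2%
- median 11: (0.1250 − 0.0042)/3.403 = 3.6%
- median 14: (0.1952 − 0.0135)/2.674 = 6.8%

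SU-AXI is a mixture of 225 untruncated and 125 truncated patients; the comparators are all truncated.

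| Assumed median | Comparators | SU-AXI mixture | Difference (months) |
|---|---|---|---|
| 8 | 7.86 | 7.95 | 0.09 |
| 11 | 10.45 | 10.80 | 0.35 |
| 14 | 12.67 | 13.49 | 0.82 |

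*Sensitivity.* If data end at month 78 (54 + 24), simulated combined PFS medians are 0.3 to 1.5 months longer in SU-AXI, with HR 0.85–0.96 and no true difference.

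**Step 4. Direction.** Incomplete or late capture pushes the HR above 1; entry route pushes it below 1.

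**Step 5. Precision after restriction.** 1.96 × √(0.25/125) = 0.088. For 230 comparators together it is 0.065, and wider for TKI or mTOR alone.

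**The case against.** The strongest reply is that no comparison is claimed. The study is uncontrolled, Protocol 8.5 says "the objective is only descriptive and the sample size will rely on the precision of the estimate", and Gap 3 promises only an overview of other sequences. That stands against saying the secondary objective cannot be met: each sequence can still be described. It does not remove the need for like measurement when the curves are listed together.

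A reader might also infer stronger points that the documents do not support:

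- **That comparators have only a survival form.** Protocol 8.2 describes it that way, but the form carries best response and a progression date at stopping, and the CRF study plan ticks tumour response for long-term follow-up. Six months is the reporting interval, not the scan interval.
- **That progression after a stop for intolerance is lost only in comparators.** SAP 6.1.1 censors axitinib patients at such a stop too.
- **That the axitinib figures in Protocol 6 size the capture problem.** "The PFS of axitinib post sunitinib was 6.5 months when assessed by investigators", against 4.8 months on independent review. That contrasts assessors. Here treating physicians assess every group.
- **That long sunitinib responders can enter only the SU-AXI curve.** Truncation removes about 1–7% of the sunitinib-start route, and it applies equally to the roughly 125 SU-AXI patients enrolled that way.
- **That the SAP has no PFS rule for TKI or mTOR.** Text on other second lines appears cut in SAP 6.1.2 and 8.2.2, so its absence cannot be called an error. Even so, no rule can recover dates that the form does not collect.
- **That a test across these groups is definitely planned.** The log-rank sentence is generic, and the visible SAP 8.2.2 assigns none to them. The conflict with SAP 4.2 still needs settling.

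**Conclusion.** The concern holds for the cross-sequence PFS display in Protocol 8.7.1. Progression with treatment continued is dated on axitinib and not on other second-line drugs, and 64% of SU-AXI patients, but no comparators, enter at second line.

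The entry effect is modest: about 0.1, 0.35 or 0.8 months in median sunitinib time for assumed sunitinib medians of 8, 11 or 14 months, with exponential times, uniform entry over 54 months and data end at month 87. The capture effect could be nil or large, depending on how completely the long-term form dates progression. The two can oppose each other, so the net bias cannot be fixed from the documents. For OS only the entry point applies, because death is recorded for all groups. The axitinib and SU-AXI primary analyses are not affected. The change is worth making because it is cheap and improves a planned secondary display.

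**What to change.** For the cross-sequence display only:

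1. Derive PFS in all three groups by one rule that both forms support: dated stop of the second-line drug for progression, or death, with the same death window and censoring rule throughout. Keep assessment-based PFS for the axitinib and SU-AXI primary endpoints.
2. Show SU-AXI separately by enrolment route, with the roughly 125 patients enrolled at sunitinib start as the like-for-like curve beside TKI and mTOR. The 225 axitinib-start patients need not be dropped. Split the SU-AXI OS curve in the same way.
3. State in SAP 8.1.2 that no log-rank test is made across second-line groups, which reconciles it with SAP 4.2 on this point.

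**Cost.** SAP wording and one extra derivation from fields already collected. The like-for-like SU-AXI curve has a half-width at the median of 0.088 instead of 0.052. The common rule does not count progression with treatment continued in any group, so its SU-AXI curve will not match the primary PFS curve and should be labelled accordingly.
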